#### **7.4 Prior and Concomitant Medications**

Number and proportion of subjects taking concomitant medications will be tabulated for the randomized sample by treatment formulation and drug classification using the WHO drug dictionary (WHODRUG Global B3, March 2020 or later) and categorized by time periods: prior to start of trial therapy, during the trial therapy, and after the trial therapy.

Proportions of subjects taking a concomitant medication of benzodiazepine will be provided by treatment formulation and/or concomitant medication. Concomitant medications for benzodiazepine are converted into lorazepam equivalent using the appropriate conversion factors. Daily dose of benzodiazepine (lorazepam or equivalent) will be summarized by treatment formulation and/or concomitant medications. The daily dose for each subject is calculated in total dosage of lorazepam or equivalent divided by the duration of IMP treatment. If subjects do not take benzodiazepine, daily dose for benzodiazepine will be considered as 0. Additionally, descriptive statistics for the duration (days) of benzodiazepine will be provided by treatment formulation and/or concomitant medications for subjects taking benzodiazepine only.

#### **7.5 Protocol Deviations**

Protocol deviations will be summarized by type of deviations and disease type. Types of deviation include deviations in entry criteria, dosing, randomization, concomitant medication, procedural, etc. In addition, a subject listing will be provided describing the deviations for each subject including protocol deviation due to outbreak of COVID-19.

During the restriction of COVID-19, the robust sampling subjects may remain in clinic until Day 225 and the sparse sampling subjects are asked to come into the clinic on days where they need to receive the once-monthly or once-bimonthly injection of IMP and the final trial visit on Day 225. On those days, all assessments for the sparse sampling subjects will occur as specified in the protocol. On visit days between dosing visits / final study visit, only safety assessments (e.g. AEs, CSSRS, BARS and AIMS) for the sparse sampling subjects will be conducted remotely (virtually) to prioritize the health and safety of these subjects. Therefore, no impact is applicable to primary PK parameters and minimal impact is on secondary PK parameters.

Protocol 031-201-00181

## 8 Safety Analyses

Safety assessments including adverse events (AEs), vital signs, ECGs, clinical laboratory monitoring (serum chemistry, hematology, urinalysis), physical examinations, EPS, VAS scores for pain perception, investigator's assessment of most recent injection site, and suicidality via the C-SSRS will be summarized for the safety sample by treatment formulation and disease type in addition to all treated subjects.

In summarizing the incidence of clinically relevant abnormalities in clinical laboratory results, vital sign measurements and ECG measurements, a subject must have had an evaluation that meets the specified criteria. Incidence rate will be calculated as the number of subjects having at least 1 abnormality in the treatment phase divided by the number of subjects in the safety sample.

Safety data collected during in-clinic visits and virtual visits are summarized together.

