**Day 29 ± 2 days (outpatient, all subjects)**

- Document birth control methods.
- Record concomitant medications and review for prohibited or restricted medications.
- Record adjustment of current oral antipsychotic, mood stabilizer, or antidepressant therapy.
- Assess and record AEs.
- Perform a urine pregnancy test (FOCBP only).
- Perform a physical examination.
- Measure weight.
- Take vital signs (systolic and diastolic blood pressure, heart rate, and body temperature).
- Administer a 12-lead safety ECG in triplicate (5 minutes apart).
- Collect clinical laboratory samples for hematology, clinical chemistry, prolactin assessment, and urinalysis.
- Administer the Since Last Visit version of the C-SSRS (predose).
- Assess EPS (SAS, AIMS, and BARS) (predose).
- Administer the PANSS (schizophrenia subjects only).
- Administer CGI-S scale and SWN-S (all subjects).
- Administer the MADRS, YMRS, and CGI-BP (bipolar subjects only).

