**Day 225/Early Termination  $\pm$  2 days (outpatient, all subjects)**

- Document birth control methods.
- Record concomitant medications and review for prohibited or restricted medications.
- Record adjustment of current oral antipsychotic, mood stabilizer, or antidepressant therapy.
- Assess and record AEs.
- Perform a urine pregnancy test (FOCBP only).
- Perform a physical examination.
- Measure weight.
- Take vital signs (systolic and diastolic blood pressure, heart rate, and body temperature).
- Administer a 12-lead safety ECG in triplicate (5 minutes apart).
- Collect hematology, clinical chemistry, and urinalysis clinical laboratory samples.
- Administer the Since Last Visit version of the C-SSRS.
- Assess EPS (SAS, AIMS, and BARS).
- Administer the PANSS (schizophrenia subjects only).
- Administer CGI-S scale and SWN-S (all subjects).
- Administer the MADRS, YMRS, and CGI-BP (bipolar subjects only).
- Draw a PK blood sample between 8 AM and 2 PM.

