### 5.1 Definition of Baseline and Last Visit

Baseline is defined as the last evaluable assessment prior to aripiprazole IMP injection while last visit is defined as the last evaluable assessment upon completion or early

Protocol 031-201-00181

termination of treatment phase. Only subjects who receive at least 1 dose of investigational medical products and have assessment at both baseline and at least 1 post-baseline visit are included in the analyses of change from baseline.

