### 8.5 Clinical Laboratory

Clinical laboratory tests include serum chemistry, hematology, urinalyses and other lab analyses. Potentially clinically relevant laboratory test abnormalities will be listed by subject and by test. Criteria for potentially clinically relevant laboratory test abnormalities are provided in [Appendix 2](#). Subjects with aspartate aminotransferase (AST) or alanine aminotransferase (ALT)  $\geq$  3 x upper limit of normal value and total bilirubin  $\geq$  2 x upper limit of normal value will be listed. The incidences of potentially clinically relevant laboratory tests abnormalities based on observations during scheduled and unscheduled post-baseline visits will be tabulated by treatment formulation and disease type. Summary statistics for clinical laboratory measurements and changes from baseline will be presented by trial visit, treatment formulation and disease type.

If laboratory tests assessments are repeated for the same mapped trial visit, the last repeated values will be used for summary tables. This is accomplished by sorting patient data by visit date and visit time (if applicable) within the same trial visit. If the lab data are recorded as ranges (i.e., including < or > limit of quantification), these data are not

Protocol 031-201-00181

included in the calculations for changes from baseline but included in the calculations for incidences.

The incidence of prolactin level above the upper limit of normal range (potentially clinically relevant change) will be calculated by treatment formulation and disease type. Summary statistics (mean, standard deviation, median, minimum, and maximum) and changes from baseline in prolactin concentration will be presented by trial visit, treatment formulation and disease type. Similar analyses will be performed for male and female, respectively. Additionally, incidences of treatment-emergent relevant changes in lipid parameters and glucose (as defined in [Table 8.5-1](#)) will be summarized by treatment formulation and disease type, though those blood samples are not required to be collected at the fasted state.

Table 8.5-1 Criteria for Treatment-emergent Relevant Changes in Lipids Parameters and Glucose		
Parameters	Baseline	Any Post-baseline
Total Cholesterol (mg/dL)		
	Normal <200	High $\geq$ 240
	Borderline 200~<240	High $\geq$ 240
	Normal/Borderline <240	High $\geq$ 240
	Normal <200	Borderline/High $\geq$ 200
	Any Value	Increased $\geq$ 40
LDL Cholesterol (mg/dL)		

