	Normal <100	High $\geq$ 160
	Borderline 100~<160	High $\geq$ 160
	Normal/Borderline <160	High $\geq$ 160
	Normal <100	Borderline/High $\geq$ 100
	Any Value	Increased $\geq$ 30
HDL Cholesterol (mg/dL)		
	Normal $\geq$ 40	Low <40
	Any Value	Decreased $\geq$ 20
Triglycerides (mg/dL)		
	Normal <150	High $\geq$ 200
	Normal <150	Very High $\geq$ 500
	Borderline 150~<200	High $\geq$ 200
	Borderline 150~<200	Very High $\geq$ 500
	Normal/Borderline <200	High $\geq$ 200
	Normal/Borderline <200	Very High $\geq$ 500
	Normal <150	Borderline/High/Very High $\geq$ 150
	Normal/Borderline /High $\geq$ 200	Very High $\geq$ 500
	Any Value	Increased $\geq$ 50
Glucose (mg/dL)		
	Normal <100	High $\geq$ 126
	Impaired Fasting Glucose 100~<126	High $\geq$ 126

Protocol 031-201-00181

Table 8.5-1 Criteria for Treatment-emergent Relevant Changes in Lipids Parameters and Glucose		
Parameters	Baseline	Any Post-baseline
	Normal/ Impaired Fasting Glucose <126	High $\geq 126$
	Any Value	Increased $\geq 10$

Note: The National Cholesterol Education Program (NCEP) Adult Treatment Program Classifications of lipids (refer to fasting lipid measurements) are used for lipid parameters and the American Diabetes Association Criteria are used for glucose.

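### SAP 8 counts untested subjects as normal in abnormality rates, which for prolactin can lower the test arm's rate alone, and one triglyceride row in Table 8.5-1 contradicts its own label

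*SAP*

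**What the plan says.** SAP 8 sets one incidence rule for clinically relevant abnormalities in laboratory tests, vital signs and ECGs: the "number of subjects having at least 1 abnormality in the treatment phase divided by the number of subjects in the safety sample". The sentence before it says that "a subject must have had an evaluation that meets the specified criteria"; this defines who counts as abnormal and does not limit the denominator. SAP 5 defines the safety sample as randomized subjects with at least one injection.

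SAP 5.1 does have an evaluable-subject rule, but for a different analysis: only dosed subjects who "have assessment at both baseline and at least 1 post-baseline visit are included in the analyses of change from baseline".

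SAP 8.5 reports the "incidence of prolactin level above the upper limit of normal range (potentially clinically relevant change") by formulation and disease type and gives it no denominator of its own. At Day 29 the protocol's activity tables say: "Collect clinical laboratory samples for hematology, clinical chemistry, prolactin assessment, and urinalysis". At Day 225/Early Termination they say only: "Collect hematology, clinical chemistry, and urinalysis clinical laboratory samples".

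SAP 7.5 describes visits under COVID-19 restrictions. Sparse-schedule subjects come to the clinic on injection days and on Day 225. On the visit days in between, "only safety assessments (e.g. AEs, CSSRS, BARS and AIMS) for the sparse sampling subjects will be conducted remotely (virtually").

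In SAP Table 8.5-1, the triglyceride row for a shift to Very High (500 mg/dL or more) from any lower category gives its baseline as "Normal/Borderline /High $\geq$ 200".

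**The concern.** A subject who was never tested after baseline cannot enter the numerator but stays in the denominator. The reported rate is therefore the rate among tested subjects multiplied by the fraction tested. If that fraction is the same in both arms, both rates are too low but their ratio is unaffected. If it differs, the comparison between arms is distorted.

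For prolactin the visit schedule and the COVID-19 rule together can produce such a difference, and it favours the test product. Safety and tolerability is the first primary objective, and these tables are presented by arm.

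The triglyceride row is a separate defect. A subject who starts at 500 mg/dL or above and stays there could be reported as a treatment-emergent shift to Very High.

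**Working it through.** **Inputs**
- Planned size: 258 subjects, 129 per arm, of whom 38 robust and 91 sparse (SAP 3).
- Dropout: 34% (SAP 4).
- Prolactin: screening, Day 1 and Day 29 only (Protocol Tables 3.7-1 and 3.7-2). The serum chemistry list in Protocol Table 3.7.6.2-1 does not include prolactin, so the Day 225/ET chemistry sample does not supply it.
- Dosing: Day 29 is an injection day for IM depot 400 mg; the second 2M LAI 960 mg injection is on Day 57 (Protocol Table 3.7-1).

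**The plan's own figures.** 170/0.66 = 257.6, rounded up to 258; 100/0.66 = 151.5, rounded up to 152; 38 + 91 = 129; 2 × 129 = 258. All reproduce. The documents state no incidence rate.

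**Who loses the Day 29 prolactin under restrictions**

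| Group | Day 29 in clinic? | Scheduled post-baseline prolactin |
|---|---|---|
| Sparse, IM depot 400 mg | yes (injection day) | kept |
| Sparse, 2M LAI 960 mg | no (remote) | lost |
| Robust, either arm | yes (may remain in clinic) | kept |

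**Loss common to both arms.** Assume the 34% dropout has a constant hazard over 225 days. The share leaving before Day 29 is 1 − 0.66^(28/225) = 5.04%, so the fraction remaining is e = 0.9496. For laboratory tests in general, if none of these subjects gives an ET sample, a true rate of 10% (assumed) is reported as 9.5% in both arms. For prolactin an ET visit does not help, because prolactin is not drawn there.

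**Loss in the 2M LAI arm only.** The sparse share is s = 91/129 = 0.7054. Let f be the share of sparse 2M LAI subjects whose Day 29 visit is remote (assumed).

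Fraction tested on 2M LAI = e × (1 − s × f); on IM depot = e. The reported ratio when true rates are equal is 1 − s × f, whatever the true rate and whatever e.

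| f | Fraction tested, 2M LAI | True 10% reported, 2M LAI | Reported, IM depot | Difference (points) | Ratio |
|---|---|---|---|---|---|
| 0.10 | 0.883 | 8.8% | 9.5% | 0.67 | 0.93 |
| 0.25 | 0.782 | 7.8% | 9.5% | 1.67 | 0.82 |
| 0.50 | 0.615 | 6.1% | 9.5% | 3.35 | 0.65 |

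The limit at f = 1 is a ratio of 38/129 = 0.295. With tested subjects as the denominator, the reported rate equals the rate among those tested at every f.

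**Triglyceride row.** The same table sets Normal below 150, Borderline 150 to below 200, High from 200 and Very High from 500 mg/dL.

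| Baseline (mg/dL) | Category | Named in the label? | Meets the printed condition? | Meets below 500? |
|---|---|---|---|---|
| 100, 149 | Normal | yes | no | yes |
| 150, 199 | Borderline | yes | no | yes |
| 200, 300, 499 | High | yes | yes | yes |
| 500, 600 | Very High | no | yes | no |

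**The case against.** The share of dosed subjects with an observed abnormality is a common safety-table definition and is applied identically to both arms. Vital signs and ECGs are repeated often. Hematology, chemistry and urinalysis are drawn again at Day 225/ET, which withdrawing subjects are encouraged to attend. This stands: outside prolactin the effect is small and roughly equal between arms.

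The size for prolactin is not in the documents. Only subjects who reach Day 29 while restrictions are in force are exposed, and unscheduled post-baseline results count towards incidence, so replacement draws would shrink the effect. This also stands: the ratios illustrate f and are not estimates of bias in this trial.

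Safety is summarized descriptively, the formal comparison is the PK ratio, and the prolactin change-from-baseline table already uses evaluable subjects. That table gives the reader a second view, but it does not correct the incidence percentage.

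An evaluable-only denominator has a risk of its own. If some 2M LAI subjects enter only through symptom-driven unscheduled draws, their rate could be inflated. This is a reason to show the number tested by arm, not to keep untested subjects as normal.

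For Table 8.5-1, each row's baseline column arguably implies its at-risk group, so the missing denominator there is a gap in wording rather than a demonstrated error. The triglyceride slip is confined to one row, since other rows cover Normal and Borderline shifting to 500 or more. A text-extraction fault cannot be wholly excluded, although the neighbouring rows read correctly.

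**Conclusion.** The concern holds. As written, SAP 8 counts untested subjects as normal for every abnormality rate. For most parameters this is minor: about 10% reading 9.5%, under the constant-hazard assumption and with no ET samples.

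For prolactin above the upper limit of normal, the schedule and the COVID-19 rule can depress the 2M LAI rate alone. The ratio falls to 0.93, 0.82 or 0.65 if 10%, 25% or 50% of sparse 2M LAI subjects miss the draw, with a bound of 0.295 if all do. These figures assume equal true rates, planned enrolment numbers and no replacement draws; the actual share is unknown.

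The triglyceride row contradicts its label. How many subjects it misclassifies depends on how many start at 500 mg/dL or above, which the documents do not give. None of this touches the PK comparison. It should be corrected because it affects how a primary safety objective is reported by arm.

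**What to change.** 1. In SAP 8, define the denominator for the abnormalities in Appendices 1 to 3 as safety-sample subjects with at least one post-baseline value of that parameter, and also a baseline value where the criterion requires a change from baseline. Show n/N by arm.
2. For prolactin, also show how many subjects in each arm have the Day 29 value and how many contribute only unscheduled values.
3. For Table 8.5-1, state the denominator as subjects who meet the row's baseline condition and have at least one post-baseline value.
4. In the triglyceride row labelled Normal/Borderline/High, change the baseline condition to below 500 mg/dL.

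The cost is SAP wording and table programming, with no new data. Denominators will differ between parameters and rows, which the n/N display makes visible.

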### 3.7.6.6.1.3 Barnes Akathisia Rating Scale

The BARS consists of 4 items related to akathisia: objective observation of akathisia by the investigator, subjective feelings of restlessness by the subject, subject distress due to akathisia, and global evaluation of akathisia. The first 3 items will be rated on a 4-point scale, with a score of 0 representing absence of symptoms and a score of 3 representing a severe condition. The global clinical evaluation will be made on a 6-point scale, with 0 representing absence of symptoms and a score of 5 representing severe akathisia. To complete this scale, subjects will be observed while they are seated and then standing for a minimum of 2 minutes in each position. Symptoms observed in other situations (eg, while engaged in neutral conversation or engaged in activity on the ward) may also be rated. Subjective phenomena are to be elicited by direct questioning.

The BARS Global Score is from the global clinical assessment of akathisia from the panel BARS in the eCRF.

Protocol 031-201-00181

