## 3 Trial Design

This is a phase 1b, open-label, multiple-dose, randomized, parallel-arm, multicenter (approximately 20 trial sites) trial in adult subjects with schizophrenia or bipolar I disorder. The trial design schematic is shown in [Figure 3-1](#).

Subjects between the ages of 18 to 64 years old, inclusively, are randomized (1:1 randomization) to receive multiple doses of 2 month (2M) long-acting injectable (LAI) 960 mg (4 injections) or aripiprazole IM depot 400 mg (8 injections) over the course of 32 weeks. Aripiprazole 2M LAI 960 mg are administered at 56-day intervals and aripiprazole IM depot 400 mg are administered at 28-day intervals (+/- 2 days). A final visit occurs 56 (+/- 2) days after the last dose of aripiprazole 2M LAI 960 mg or 28 (+/- 2) days after the last dose of aripiprazole IM depot 400 mg. The randomization is

Protocol 031-201-00181

stratified by PK sampling schedules (robust sampling schedule or sparse sampling schedule) and disease type (schizophrenia or bipolar I disorder). If enrollment of the number of subjects required for the robust sampling schedule is completed, the robust sampling trial sites may enroll new subjects to the sparse sampling schedule.

The trial consists of a screening period of up to 30 days, a treatment period of 169 ( $\pm 2$ ) days, and a follow-up period of 56 ( $\pm 2$ ) days after administration of the final dose for the aripiprazole 2M LAI 960 mg treatment group, or a treatment period of 197 ( $\pm 2$ ) days, a follow-up period with 28 ( $\pm 2$ ) days after administration of the final dose for the aripiprazole IM depot 400 mg treatment group. Individual participation is approximately 255 ( $\pm 2$ ) days.

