### **8.8 Extrapyramidal Symptoms Scales**

Extrapyramidal Symptoms (EPS) rating scales include the Simpson-Angus Scale (SAS), Barnes Akathisia Rating Scale (BARS) and Abnormal Involuntary Movement Scale (AIMS). The variables to be analyzed are,

- Change from Baseline in SAS Total Score,
- Change from Baseline in BARS Global Score,
- Change from Baseline in AIMS Movement Rating Score.

The SAS total score (range 10 - 50) is the sum of the rating scores for 10 items from the SAS panel in the Case Report Form (CRF). The BARS global score (range 0 - 5) is derived from the global clinical assessment of akathisia from the BARS panel in the CRF. The AIMS movement rating score (range 0 - 28) is the sum of the rating scores for facial and oral moments (i.e., item 1 - 4), extremity movements (i.e. item 5 - 6), and trunk movements (i.e. item 7). A missing value of any item for the SAS or the AIMS movements scale could result in a missing SAS total score or AIMS movement rating

Protocol 031-201-00181

score. LOCF missing data imputation will be performed those scores. Descriptive statistics of the EPS rating scales for both LOCF and OC data and the mean changes of the scales from baseline will be reported by trial week, treatment formulation and disease type.

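### Under the COVID-19 visit rule, sparse-schedule 960 mg subjects have EPS ratings remotely at Weeks 4, 12, 20 and 28 while 400 mg subjects are rated in clinic, and the SAP pools the two modes

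*SAP*

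**What the plan says.** SAP 7.5 sets the rule for the restriction period. In it, "sparse sampling subjects are asked to come into the clinic on days where they need to receive the once-monthly or once-bimonthly injection of IMP", plus the final visit on Day 225. At the visits between, "only safety assessments (e.g. AEs, CSSRS, BARS and AIMS) for the sparse sampling subjects will be conducted remotely". For the other stratum, "the robust sampling subjects may remain in clinic until Day 225". The same section judges the effect of the rule on PK parameters and does not mention its effect on safety data.

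The arms differ in when they are dosed. SAP 3 says "Aripiprazole 2M LAI 960 mg are administered at 56-day intervals", against every 28 days for 400 mg. The sparse schedule (Protocol Tables 3.7-1 and 3.7.3-2) nevertheless plans SAS, AIMS and BARS in both arms on Days 8, 15, 22, 29, 57, 85, 113, 141, 169, 197 and 225.

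For analysis, SAP 8 states: "Safety data collected during in-clinic visits and virtual visits are summarized together". SAP 8.8 reports the EPS scales descriptively by trial week, formulation and disease type, for both LOCF and observed-case (OC) data. On missing SAS and AIMS scores it says: "LOCF missing data imputation will be performed those scores". Neither section separates results by rating mode or adds a sensitivity summary.

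**The concern.** The EPS scales are among the primary safety variables (Protocol 3.5.1.1, SAP 6.1), and Protocol 1.4 lists akathisia among the most frequent adverse reactions. How a scale is administered can affect its score. For BARS, Protocol 3.7.6.6.1.3 requires that "subjects will be observed while they are seated and then standing for a minimum of 2 minutes in each position". AIMS (3.7.6.6.1.2) relies on unobtrusive observation at rest. SAS (3.7.6.6.1.1) includes arm dropping, shoulder shaking, and elbow and wrist rigidity.

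Missing or remote visits usually fall on both arms alike. Here the rule follows each arm's own injection calendar, so at certain weeks mode is tied to arm by construction, and randomization cannot balance it. A reader comparing the arms at those weeks in the pooled table could not tell a formulation difference from a mode difference, or from the absence of one hidden by the other.

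**Working it through.** **Sparse share.** The plan's enrolment figures reproduce at 34% dropout: 170/0.66 = 257.6, so 258; 120/0.66 = 181.8, so 182 sparse; 50/0.66 = 75.8, so 76 robust; and 182 + 76 = 258. Per arm, 91 of 129 are sparse: 91/129 = 0.705.

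**Visit count.** A sparse subject's EPS visit is remote under the rule if it is neither an own-arm injection day nor Day 225. Injection days are 1, 57, 113 and 169 for 960 mg, and 1, 29, 57, 85, 113, 141, 169 and 197 for 400 mg. Weeks follow SAP Table 5.2-3.

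| EPS visit (Day) | Week | 960 mg sparse | 400 mg sparse |
|---|---|---|---|
| 8, 15, 22 | 1, 2, 3 | remote | remote |
| 29 | 4 | remote | clinic |
| 57 | 8 | clinic | clinic |
| 85 | 12 | remote | clinic |
| 113 | 16 | clinic | clinic |
| 141 | 20 | remote | clinic |
| 169 | 24 | clinic | clinic |
| 197 | 28 | remote | clinic |
| 225 | 32 | clinic | clinic |

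If the rule applies throughout, remote EPS visits from Day 29 number 4 of 8 for 960 mg and 0 of 8 for 400 mg. Over all postbaseline visits they are 7 of 11 and 3 of 11; from Day 57, 3 of 7 and 0 of 7.

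**BARS and AIMS.** Both are named as remote assessments. Let f be the share of sparse 960 mg subjects under restrictions at a given visit, and d the average shift in score caused by remote rating. Neither is given in the documents. With equal dropout in the two strata, and robust subjects rated in clinic, the arm difference at Weeks 4, 12, 20 and 28 moves by 0.705 × f × d. For an assumed d of 1 point in either direction:

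| f | Shift (points) |
|---|---|
| 0 | 0 |
| 0.10 | 0.07 |
| 0.25 | 0.18 |
| 0.50 | 0.35 |
| 1 | 0.71 |

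**SAS.** It is not named among the remote assessments. If it is skipped at remote visits, LOCF fills Weeks 12, 20 and 28 in affected 960 mg subjects from Days 57, 113 and 169, each 28 days earlier and predose, while 400 mg has values observed in that week. Week 4 differs. SAP 5.3 does not carry baseline forward, so a subject restricted from the start has no SAS to carry and is simply missing.

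**LOCF for BARS and AIMS.** A 960 mg subject whose last rating was remote carries that value into later weeks, including Weeks 8, 16, 24 and 32. Only OC data are balanced for mode at those weeks under the rule.

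**The case against.** The strongest reply is that little depends on this comparison. EPS is only described: there is no test, model or decision rule, and the formal similarity criterion is PK only. Results are already shown week by week, so the four later weeks with both arms in clinic can be read from the planned tables. OC summaries are planned beside LOCF, and a SAS that was not done is absent from OC. COVID-19 deviations are listed by subject (SAP 7.5), and EPS-related adverse events and anticholinergic use are tabulated (SAP 8.10). All of this stands and limits the consequence. It does not tell a reader which ratings at Weeks 4, 12, 20 and 28 were remote, and it does not make OC the leading summary.

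Three stronger readings are tempting, and the documents support none of them.

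- A reader might infer that remote rating misses akathisia and so favours 960 mg. Nothing in the documents says so. Remote contact could include video, and over-rating, under-rating or no shift are all possible.
- A reader might infer that these are the visits at which the 960 mg concentration is highest. Protocol 1.3 gives single-dose median tmax of 25.1 days for 780 mg and 41.0 days for 1200 mg, with a secondary peak. It gives no value for 960 mg or for steady state.
- A reader might take it as settled that SAS was skipped. The remote list in SAP 7.5 is introduced as examples, so that part of the point is conditional.

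**Conclusion.** The point holds as a limit on interpretation. For sparse subjects under restrictions, rating mode is tied to arm at Weeks 4, 12, 20 and 28, and the pooling rule hides it. In OC data the problem is confined to those four weeks, to sparse subjects and to visits during restrictions. LOCF can spread it further.

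Its reach runs from none to about 70% of the 960 mg arm at those weeks. The upper end requires every sparse 960 mg subject to be restricted at the visit. The direction is undocumented, and no formal test is affected. The conclusion assumes that SAP 7.5 is applied as written, with clinic attendance following each subject's own injection calendar. The SAS part also assumes that SAS is not done remotely. This is a worthwhile, inexpensive improvement and does not threaten the primary PK conclusions.

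**What to change.** In SAP 8 and 8.8:

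- Record the mode (in clinic or remote) of each EPS rating, and state whether SAS is attempted remotely.
- Add an OC summary of SAS, BARS and AIMS limited to in-clinic ratings, read between arms mainly at Weeks 8, 16, 24 and 32. At the other four weeks this summary loses the restricted sparse 960 mg subjects, so the arms would differ in their mix of strata.
- Keep the planned tables at Weeks 4, 12, 20 and 28, add the number of remote ratings by arm, and note that mode and arm cannot be separated there in sparse subjects. A table split by mode would not solve this, because it has almost no remote 400 mg ratings for comparison.
- In the LOCF summary, do not carry remote BARS or AIMS values into in-clinic weeks, or SAS into weeks whose visit was remote. Alternatively, declare OC the leading EPS summary.

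The cost is SAP wording, one flag variable and a little more output, with fewer mode-balanced time points for comparing the arms. No new assessments are needed.
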